6. STUDY OBJECTIVES

6.1. Primary Objective

To assess the efficacy of 2 doses of NTRA-2112 as compared to placebo on intestinal malabsorption in preterm infants as measured by the time to full enteral feeding.

Note: days to full enteral feeding will be regarded as the time to 3 consecutive days consumption of at least 150 ml/kg/day enteral feeding.

6.2. Secondary Objectives

Key secondary objective:

To assess the effect of 2 doses of NTRA-2112 compared to placebo on the number of days to achieve discharge from hospital or readiness for discharge, whichever occurs first.

Readiness for discharge from hospital defined as achieving all of the below:

- 1. Infant weight ≥ 1800g
- 2. Stable body temperature
- 3. Capable of oral feeding (reached full enteral feeding and not dependent on PN).

Other secondary objectives:

To compare 2 doses of NTRA-2112 to placebo with respect to the following:

- 4. Growth parameters (g/kg/day)
- 5. Change in Z-score at 6, 8 and 10 days from initiation of treatment
- 6. Gain in body weight during the treatment and follow-up periods
- Number and percentage of infants reaching full enteral feeding within 6, 8, and 10 days from initiation of treatment
- 8. Total number of days receiving parenteral nutrition
- 9. Number of days to 120Kcal/kg/day
- 10. Number of days to wean-off PN4

Exploratory secondary objective:

 Number of days to end gastric residuals over 2 ml/measurement according to the feeding protocol (Appendix A).

⁴ Wean off PN is defined as complete cessation of PN support.

6.3. Safety Objective

To compare 2 doses of NTRA-2112 to placebo in preterm infants.

STUDY DESIGN

[figure not shown]
The study is designed as a multi-center, double-blind, randomized, three-arm, parallel-group, placebocontrolled study to assess the efficacy and safety of NTRA-2112.

Infants will be enrolled within 5 days from birth (at least 6 hours post birth and up to 120 hours post birth) and will be treated for 28 days or until hospital discharge (whichever comes first). The study also includes a follow-up period up to 24 months corrected age. Figure 1 and Appendix B includes a detailed study flow diagram.

Full enteral feeding is defined as reaching 3 consecutive days in which the infant consumed at least 150 ml/kg/day of enteral nutrition.

Enrolled infants will be under supervision at a NICU.

Figure 1: Study Flow Diagram

8. STUDY POPULATION

8.1. Study Participants

Infants up to 5 days old (up to 120 hours post birth), born between 26 and up to 32 weeks of pregnancy, weighing at least 500g at birth, and who meet enrolment criteria are eligible for this study. Their parents or legal guardian will be asked to sign an informed consent form (ICF) for the study. Only single or twin births will be eligible, not triplets or higher. Upon parents' signature of the informed consent form, the infants will be screened for eligibility. Once eligibility has been confirmed, the infant will randomly be assigned to one of three treatment groups: low dose or high dose of study medication (treatment A & B) or placebo (treatment C). The study drug (NTRA-2112 or placebo) will be administered with the infant's enteral feeds.

Eligible infants who are enrolled into the study will be assigned a treatment group randomly. Eligible twins will automatically be assigned to the same treatment group.

All enrolled infants, including both members of a pair twins, should undergo all procedures described in this and the following section.

Pre-term infants will be treated at a NICU and will be under constant supervision during the hospitalization period until discharge home.

8.2. Inclusion Criteria

- Male or female pre-term infants 26 and up to 32 weeks gestation (32 weeks + 0 day maximum).
 - Gestational age matching (±2 weeks) between maternal dates and/or early antenatal ultrasound*.
- Birth weight ≥ 500g.
- 3. Singleton, or twin birth.
- 4. Postnatal age up through and including Day 5 (up to 120 hours post birth).
- Fraction of inspired oxygen ≤ 0.60 at enrolment.
- Subjects must demonstrate cardiovascular stability at time of enrolment and would be considered unstable if they require >40% oxygen with blood pressure support and the need for umbilical artery cauterization.
- 7. Infant is able to tolerate enteral feed.
- 8. Infant is expected to wean off PN at the primary hospital.
- 9. Informed consent form (ICF) signed by parents or legal guardian.
- 10. In the Investigator's opinion, the infant is able to comply with the study procedures and sufficiently stable to partake in the trial as required until trial completion. * If both exist and difference > 2 weeks, based on early antenatal ultrasound

8.3. Exclusion Criteria

- 1. Complete enteral feeding.
- 2. Major congenital malformation (e.g., Infants with genetic, metabolic, and/or endocrine disorder diagnosed before enrolment).
- 3. High index of suspicion of infection before enrolment**
- 4. Intra-uterine growth retardation (IUGR) defined as either weight for gestational age less than the third percentile or less than the 10'th percentile with Doppler abnormalities in utero***.
- Confirmed necrotizing enterocolitis (NEC).⁵
- 6. Maternal diabetes (Type I/II or gestational) requiring insulin during pregnancy or in mothers past medical history.
- 7. Hyperinsulinemia requiring glucose administration of more than 12mg/kg/min at randomization.
- 8. Any systemic insulin administration at randomization.

⁵ NEC is characterized by the sudden onset of gastrointestinal distress that may include symptoms such as vomiting, abdominal distention, bloody stools, or dilated loops of bowel that leads to cessation of enteral feedings.

[figure not shown]

- 9. Nothing per os (NPO) for any reason at the study entry.
- 10. Heart and chest compression or any resuscitation drugs given to the infant during delivery.
- 11. Subjects at risk for significant GI complications such as twin-to-twin transfusion syndrome (TTTS) or monochorionic monoamniotic twins.
- 12. Participation in another interventional clinical study that may interfere with the results of this trial **Defined as positive blood culture, Leukocytosis >30,000 and Leukopenia <4,000.
- ***According to Fenton preterm growth chart (see Appendix D). If no Doppler in utero is available for infants with IUGR between third and 10'th percentile of Fenton preterm growth charts, infant is eligible to participate in the study.

[figure not shown]
9.	
**	~
9	

[figure not shown]

.

						- 22
					25	56
				2.		
			I	2		
		I				
		1		1	1	
		Ī		Ī	1	•
				J.		
	 	,,,				
				22	2	
I.						

				1	2	
					30	
		I				
					0	,
		I	I			
					1	
					1	
		2.				
				7.2		
	Ĭ					
	40					
					5	
						I

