Monitoring of glucose levels will be performed during the treatment period.

NUMBER OF CENTERS

Approximately up to 40 sites worldwide (European countries, United States of America, Israel, and possibly other countries).

3. **DEFINITIONS**

Trophic feeding

Cardiovascular stability	Normal pulse, blood pressure, and breath; clinically not significant
	cardiovascular status as determined by the PI
Day (24 hours)	From 00:00/12:00am until 23:59/11:59pm
Enteral feeding (EN)	A method of nutrition delivery where fluid is given directly into the
	gastrointestinal tract.
Full enteral feeding	The infant consumes at least 150 ml/Kg/day of enteral feeding for 3
	consecutive days.
Full term pregnancy (for	TO SECURITION OF THE SECOND
The state of the s	40 weeks gestation should be considered a full term pregnancy.
calculating corrected age)	
Gastric residual	Any leftover nutrition in the stomach that was not digested or
	absorbed by the body. In hospitals where it is captured as standard
	of care, when the infant is treated with an orogastric tube, before
	every meal the nurse checks if any residuals were not absorbed and
	left in the stomach from the prior meal.
Gestational diabetes	Diagnosis glucose values for gestational diabetes according to WHO:
	Oral glucose tolerance test (OGTT) 75 g
	Fasting: 126 mg/dl
5	Two hours: 140 mg/dl
High index of suspicion for	Occurrence of one or more of the following conditions:
infection	(1) Positive blood culture;
	(2) Leukocytosis > 30,000 (when accompanied by a negative
, r	culture
-	rosult);
er en	(3) Leukopenia < 4,000
Hyperglycemia	Blood glucose level above 150 mg/dl
Hypoglycemia	Blood glucose level below 40 mg/dl
Intra-uterine growth Weight f	or gestational age less than p3 or less than p10 with Doppler retardation
(IUGR) abnormalities in	utero.
Necrotizing Enterocolitis (NEC	NEC is characterized by the sudden onset of gastrointestinal distress
	that may include symptoms such as vomiting, abdominal distention,
	bloody stools, or dilated loops of bowel that leads to cessation of
	enteral feedings.
Parenteral nutrition (PN)	Nutrition provided intravenously.
Total parenteral nutrition	
	TPN is a way of supplying all the nutritional needs of the body by
(TPN)	bypassing the digestive system and dripping nutrient solution directly
	into a central vein.

Feeding of small quantities.

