Insulin stimulates intestinal epithelial cell proliferation, and ileal lactase activity is increased when porcine insulin is added to newborn piglets' feedings (4, 10). Shulman, et al. demonstrated that enteral insulin administration may be of benefit in reducing feeding intolerance in preterm infants (11). Thus, orally administered insulin is expected to demonstrate a beneficial influence on gut development.

The NTRA-2112 powder is mixed with saline, preterm infant's formula, own mother's breast milk or pasteurized breast milk (donor breast milk) for enteral administration. Natural insulin activity level is lost in pasteurized breast milk and absent in formula. The final insulin concentration obtained with NTRA-2112 in the infant's nutrition is physiological and within the range of known local gut exposure to insulin levels in amniotic fluid and own mother's milk.

During the past decade neonatologists have made major efforts to reduce feeding intolerance and time to full enteral nutrition because of the importance of reducing complications and enhancing development of vital organs in preterm infants. Major efforts include the introduction of donor breast milk (DBM) as well as improvement of preterm infant formula composition and other supplementations to mother's milk. NTRA-2112 is aimed at further improving preterm infant progression to enteral autonomy, reducing risks and improving infant development in this crucial window of opportunity.

Preliminary data in preterm infants receiving 4 IU/kg/day insulin enterally from 4 to 28 days of age, suggest that enteral insulin administration increases lactase activity and may be of benefit in reducing feeding intolerance without inducing hypoglycaemia or other adverse effects (11).

The administration of insulin to preterm infants' enteral nutrition proposed in this study will allow assessment of the influence of insulin on gastrointestinal maturation and on blood levels of lipids and glucose.

As described in the following paragraphs, administration of oral insulin to preterm infants, low birth weight infants, humans and animals, at concentrations up to 1,000 times higher than those proposed in this study, demonstrated the safety of oral insulin administration.

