9.5.2. Premature Study Termination

The study subjects are expected to experience many adverse events, including severe adverse events related to premature birth, invasive surgery, or other underlying conditions including potential to develop NEC. NEC is characterized by the sudden onset of gastrointestinal distress that may include symptoms such as vomiting, abdominal distention, bloody stools, or dilated loops of bowel that leads to cessation of enteral feedings. Therefore, all safety concerns potentially leading to study termination will be referred to the Data Monitoring Committee (DMC), which is responsible for a formal assessment of the safety of the study. This Board will propose the appropriate course of action to the Sponsor.

Individual Events:

Any of the following individual events would be referred by the study Medical Monitor to the DMC chairman for review, who may decide that the events warrant a full DMC review. The DMC will review these events unblinded to fully evaluate the potential risk to subjects in this trial. Given this is a blinded trial, the DMC review is required to consider if the events, both serious and related non-serious events, are occurring more frequently in the active arms and to judge whether there is a meaningful likelihood that these events are drug-related. The DMC may recommend to the Sponsor to stop the study, or any portion of it, at any time for safety reasons on the basis of their review. Individual events that may trigger a DMC review based on individual cases:

- Two or more cases of Grade 3 or greater allergic reactions or anaphylaxis, that the investigator deems as possibly related to study medication;
- Any case of autoimmune disease associated with neutralizing antibodies to insulin and where other related causes, such as Type I diabetes, are ruled out;
- Two or more cases of persistent Grade 3 or greater hypoglycemia that is non-responsive to treatment within 72-hours and reoccurs after temporary discontinuation of study medication and re-challenged.

Further, the Medical Monitor will be responsible for review of all reported SAEs in an ongoing manner. Any SAE that is deemed potentially related to study medication, or of particular concern by the Medical Monitor, will also be sent to the DMC Chairman for review within 15 days. The DMC Chairman may decide to bring any individual SAE event that may be related and of concern to the full DMC for review.

Collective Events:

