 - Hypothermia in a preemie can lead to breathing problems and low blood sugar levels. In addition, a preemie may use up all of the energy gained from feedings just to stay warm, not to grow bigger. That is why smaller preemies require additional heat from a warmer or an incubator until they are larger and able to maintain body temperature without assistance.
- Gastrointestinal problems. Preemies are more likely to have immature gastrointestinal systems, leaving
 them predisposed to complications such as necrotizing enterocolitis (NEC). This potentially serious
 condition, in which the cells lining the bowel wall are injured, can occur in premature babies after they
 start feeding. Premature babies who receive only breast milk have a much lower risk of developing NEC.
- Blood problems. Preemies are at risk of blood problems such as anemia and infant jaundice. Anemia is a common condition in which the body does not have enough red blood cells. While all newborns experience

a slow drop in red blood cell count during the first months of life, the decrease may be greater in preemies, especially if the baby has a lot of blood taken for lab tests.

Infant jaundice is a yellow discoloration in a newborn baby's skin and eyes that occurs because the baby's blood contains an excess of a yellow-colored pigment from the liver or red blood cells (bilirubin).

- Metabolism problems. Premature babies often have problems with their metabolism. Some preemies
 may develop an abnormally low level of blood sugar (hypoglycemia). This can happen because preemies
 typically have smaller stores of glycogen (stored glucose) than do full-term babies and because preemies'
 immature livers have trouble converting stored glycogen into glucose.
- Immune system problems. An underdeveloped immune system, common in premature babies, can lead
 to infection. Infection in a premature baby can quickly spread to the bloodstream causing sepsis, a
 lifethreatening complication.

Long-term complications

In the long term, premature birth may lead to these complications:

- Cerebral palsy. Cerebral palsy is a disorder of movement, muscle tone or posture that can be caused by
 infection, inadequate blood flow or injury to a preemie's developing brain either during pregnancy or while
 the baby is still young and immature.

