1.2.4 Safety Endpoints

- Adverse events (AEs)
- Serious Adverse events (SAEs), including NEC and death
- Blood glucose level
- Complete blood count
- Anti-Insulin antibodies
- Frequency and consistency of stools
- Respiration status
- Lab measures
- Vital signs

Confidential Page 11 of 40

Statistical Analysis Plan V1.3 SAP Date: 06APR2018

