2.2.1.3.2 Ranks for NEC and Death of Subjects

Infants who experience NEC (Necrotizing Enterocolitis) will be assigned ranks of NFE according to censoring times of 29 days and infants who die will be assigned ranks of NFE according to censoring times of 30 days. The individual ranks among subjects experiencing NEC and the individual ranks among subjects who die will be handled according to Section 1.3.3.

Since it can take significantly longer than 28 days to be discharged or being ready to be discharged, infants who experience NEC (Necrotizing Enterocolitis) will be assigned ranks of NRD according to censoring times of 181 days and infants who die will be assigned ranks of NRD according to censoring times of 182 days. The individual ranks among subjects experiencing NEC and the individual ranks among subjects who die will be handled according to Section 1.3.3.

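### NEC has no confirmatory case definition in the visible text, yet the label alone can place an infant next to death, most clearly for NRD (Day 181)

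*Protocol*

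**What the plan says.** **Definition.** Protocol Section 3 states that "NEC is characterized by the sudden onset of gastrointestinal distress". The footnote to exclusion criterion 5 in Protocol 8.3 completes the description: "symptoms such as vomiting, abdominal distention, bloody stools, or dilated loops of bowel that leads to cessation of enteral feedings". Protocol 9.5.2 repeats it. Exclusion 5 itself asks for confirmed NEC, but its footnote is this same list. Appendix E describes a condition "in which the cells lining the bowel wall are injured" and gives no rule for diagnosing it.

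**Use as a safety outcome.** SAP 1.2.4 lists "Serious Adverse events (SAEs), including NEC and death", and Protocol 12.2.4 compares NEC incidence between arms.

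**Use in ranking.** For the key secondary endpoint, SAP 2.2.1.3.2 says that "infants who experience NEC (Necrotizing Enterocolitis) will be assigned ranks of NRD according to censoring times of 181 days"; deaths are placed at 182. For NFE the same section uses Day 29 for NEC and Day 30 for death. The log-rank analysis in SAP 2.2.1.4, the tie-breaking analysis in 2.2.1.7 and the other days-to-event endpoints in 2.2.2 also give NEC its own censoring time or rank.

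**A limiting condition stated elsewhere.** SAP 1.3.3 gives the NEC rank to infants who do not achieve full enteral feeding and also experience NEC. Protocol 12.3 gives it to infants who fail to achieve EN because of NEC. SAP 2.2.1.3.2 does not repeat either condition. It refers to 1.3.3 for the individual ranks among NEC cases.

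**The concern.** In the visible description every sign is optional and the signs are joined by an or. The one firm element is that feeds stop. An acute episode of distention with a feeding pause, and no evidence of bowel injury, can fit it. A rank next to death presupposes serious disease, and the description does not secure that.

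The point carries more weight in this trial because the protocol cites evidence that "enteral insulin administration may be of benefit in reducing feeding intolerance in preterm infants". If symptom-only episodes are labelled NEC at equal rates in all arms, the rank comparison is diluted and power is lost. If the drug reduces them, part of the rank difference would come from feeding pauses scored close to death. In both cases the NEC safety comparison mixes bowel disease with interrupted feeds.

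**Working it through.** **1. The plan's sample size.** Inputs from SAP 1.3.3: means 8.0 and 6.6 days (difference 1.4), SD 3.5, two-sided 5%, 85% power by t-test. The normal formula gives 113 per group and the noncentral t gives 114; the SAP states 115. At the protocol's 2.5% level the same methods give 135 and 136; Protocol 12.3 states 136. The sample-size arithmetic is not in question.

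**2. NRD, by reading.** SAP 2.2.1.3.2 places every infant who experiences NEC at 181 and attaches no condition about actual discharge. Section 4 of the SAP says that NRD may be observed up to 180 days. An infant labelled NEC who goes home on Day 45 (an illustrative day) has an observed value of 45 and a ranked value of 181, a shift of 181 - 45 = 136 days. That puts the infant behind every infant discharged by Day 180. The condition in SAP 1.3.3 concerns full enteral feeding and is written for NFE; it says nothing about discharge.

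**3. NFE if 2.2.1.3.2 overrides an achieved full feed.** The documents give no rate of symptom-only episodes, so a share m of each arm is assumed to be moved to Day 29.

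- Rank effect without mislabelling: θ = Φ(1.4 / (3.5 × √2)) = 0.6114, an excess over 0.5 of 0.1114.
- With equal shares: θ′ - 0.5 = (1 - m)² × (θ - 0.5).
- Null standard error at n = 115: √((2n + 1) / (12n²)) = √(231 / 158,700) = 0.03815.
- Power = Φ((θ′ - 0.5) / 0.03815 - 1.96).

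| m per arm | (1 - m)² | θ′ - 0.5 | Power, formula | Power, simulation |
|---|---|---|---|---|
| 0 | 1.000 | 0.1114 | 0.83 | 0.83 |
| 3% | 0.941 | 0.1048 | 0.78 | 0.79 |
| 5% | 0.903 | 0.1005 | 0.75 | 0.76 |
| 10% | 0.810 | 0.0902 | 0.66 | 0.65 |

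The simulation used 6,000 trials per row, whole-day normal NFE clipped to Days 1 to 28, and a two-sided Wilcoxon test at 0.05. Repeat runs agreed to within about 0.015. A van Elteren simulation with six strata and skewed (gamma) NFE started higher and fell in the same way: 0.91 with no mislabelling, then 0.87, 0.83 and 0.74 at 2%, 5% and 10%.

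**4. Unequal shares, same reading.** With 10% on placebo and 5% on drug, simulated power is 0.89, above the 0.83 without such episodes. If NFE itself does not differ, θ′ - 0.5 = (m_placebo - m_active) / 2. For 7% and 2% this is 0.025, and 0.025 / 0.03815 = 0.655. The rejection rate is Φ(0.655 - 1.96) + Φ(-0.655 - 1.96) = 0.10. With equal shares of 5% it stays at 0.05.

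**5. NFE if SAP 1.3.3 governs.** Only infants who never reach full feeding can take the NEC rank. Under a gamma distribution with the placebo mean and SD, the probability that NFE exceeds 28 days is about 0.0001, so essentially no infant moves even at m = 10%. In the 2.2.1.7 analysis, an infant who does not reach full feeding is placed at Day 28 without NEC and Day 29 with it, a shift of one day.

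**The case against.** The strongest objection is that the NFE harm depends on one reading. SAP 1.3.3 and Protocol 12.3 restrict the NEC rank to infants who do not reach full feeding, and 2.2.1.3.2 points back to 1.3.3. An infant who pauses feeds and then sustains 150 ml/kg/day for three days would keep the observed NFE. This stands, and the power figures hold only on the other reading. It does not settle the matter, because 2.2.1.3.2 refers to 1.3.3 only for ordering within the NEC group, so a programmer could implement either rule.

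A second objection is that the Day 45 example is partly a question of precedence: an infant with proven NEC who goes home on Day 45 would also be ranked at 181. That is correct, and a tighter case definition alone would not cure it.

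Third, the text says what NEC is characterized by; it does not instruct sites to code every such episode as NEC. Investigators assess adverse events, the sponsor reviews those assessments, and the Medical Monitor reviews SAEs (Protocol 11.3, 11.4 and 9.5.2). These checks lower the risk of mislabelling but supply no written criterion for ranking. Protocol 9.1 to 9.4, the procedures table, Appendix A and SAP 2.2.1.3.1 are not visible and could contain one.

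Some stronger readings are tempting and are not supported:

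- A reader might infer that NEC takes the worst rank. It is second worst; death is worst.
- A reader might take it as documented that feeding intolerance presents in the same way as this description. The visible text does not say how feeding intolerance presents, so the overlap is clinical inference.
- A reader might infer an inflated type I error. Equal mislabelling leaves it near 5%. The unequal scenarios assume that the arms truly differ in episode rates, so they change what a positive result means and do not show a false-positive rate.

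**Conclusion.** The point holds within limits. In the visible text NEC has no confirmatory definition for on-study use, and the label can set an infant's rank on the primary and key secondary endpoints.

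The exposure is clearest for NRD, where it follows from the wording of SAP 2.2.1.3.2 and could be as large as Day 45 becoming Day 181 for a single infant. No trial-level size can be given for NRD, because the documents give no NEC or mislabelling rate.

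For NFE the size lies between near zero, if 1.3.3 governs, and a fall in power from about 0.83 to 0.79, 0.76 or 0.65, if 2.2.1.3.2 overrides an achieved full feed and 3%, 5% or 10% of each arm are affected. The SAP aims for at least 80% with the van Elteren test. The 3% to 10% range is an assumption, and the conclusion could change if the missing sections hold diagnostic criteria. This should be corrected before unblinding; it does not by itself invalidate the primary analysis.

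**What to change.** 1. For the ranking rules (SAP 1.3.3, 2.2.1.3.2, 2.2.1.7 and 2.2.2) and the NEC safety count, count as NEC only cases supported by radiographic, surgical or autopsy evidence already in the record. Capture this in one eCRF or SAE field, completed before unblinding. This is an analysis definition and leaves clinical care unchanged.
2. Infants with symptom-only episodes keep their observed NFE and NRD. Those who do not reach the endpoint are handled like any other infant without NEC who does not reach it.
3. Reconcile SAP 1.3.3 with 2.2.1.3.2 by stating, separately for NFE and NRD, whether an achieved full feed or discharge takes precedence over a NEC label.
4. Report symptom-only feed-stopping episodes by arm as a separate line, and run the all-reported-NEC ranking as a sensitivity analysis.

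The cost is definition wording, one data field filled from existing reports, and one extra analysis. The downside is a smaller NEC category, and some true cases without imaging may be missed. The sensitivity analysis keeps those cases in view.
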